10.1. Background

Several clinical trials (including MIRCLE¹, MIRACLE-ICD², CONTAK-CD³, MUSTIC⁴, PATH-CHF⁵, COMPANION⁶, MADIT CRT⁷, and CARE-HF⁸) have demonstrated the benefit of cardiac resynchronization therapy (CRT) among patients with moderate to severe heart failure (HF) with a prolonged QRS duration and depressed Left Ventricular (LV) function.

Approximately 5.7 million people in the United States (US) are living with HF⁹. Heart Failure may be a chronic condition which causes the heart to not pump oxygenated blood efficiently through the body due

to stiffening of the heart muscle. Heart Failure may affect one or both sides of the heart. It is most often caused by coronary artery disease (CAD) or uncontrolled hypertension (HTN). Patients who suffer from HF experience a variety of different symptoms including most often fatigue, cough, and shortness of breath, swollen feet (edema) and weight gain.

Heart Failure is treated with medications and sometimes cardiac devices (i.e. pacemaker or defibrillator with CRT). Medications work to relieve symptoms and reverse the effects of HF. Cardiac Resynchronization Therapy devices treat HF by synchronizing the left and right ventricles of the heart which improves the heart's ability to pump oxygenated blood to the body.^{10 11 12 13 14 15 16 17 18 19 20 21}

Cardiac Resynchronization Therapy devices are made up of 4 main components; the can or battery, a Right Atrial (RA) lead, a Right Ventricular (RV) lead, and a Left Ventricular (LV) lead.

The LV lead specifically is important at maintaining ventricular synchrony. In 2014, Medtronic released the Attain® Performa™ family of LV leads (models 4298, 4398 and 4598). The three different shapes of these leads (double canted, straight, and S-shaped) were designed to enable the lead to be passively fixed within different anatomies of coronary vessels. In addition, the 4 strategically placed electrodes on the lead were designed to offer 16 different electrical vector programming configurations.

Medtronic also released the Attain Stability bipolar LV lead (Model 20066/4796) (CE Mark approved in September 30, 2013) in Europe. This lead has a side helix which enables it to be actively fixated to the vessel wall. The active fixation is an advantageous component in vessels that are wide or have short take-offs. The next generation of LV lead is known as the Attain Stability™ Quad MRI SureScan LV lead (Model 4798). This is a quadripolar lead similar to its Attain Performa predecessor leads and has a side helix for active fixation like the Attain Stability bipolar lead.

10.2. Purpose

The Attain Stability Quad Clinical Study is a prospective, non-randomized, multi-site, Investigational Device Exemption (IDE), interventional clinical study. The purpose of this clinical study is to evaluate the safety and efficacy of the Attain Stability™ Quad MRI SureScan LV Lead (Model 4798). This study will not be considered investigational in geographies with CE Mark of the Attain Stability™ Quad MRI SureScan LV lead (Model 4798). However, data collected from all study subjects will be represented in the final clinical report and the PMA Supplement (PMA-S) to the Attain Ability Model 4196 Original PMA (P080006, approved April 7, 2009).

Subjects successfully implanted with the Attain Stability Quad MRI SureScan LV Lead (Model 4798) will be followed at implant, three months, six months and every six months thereafter until FDA approval is obtained or until study closure, whichever comes first.

11. Objectives and Endpoints

11.1. Objectives

11.1.1. Primary Objective(s)

Primary Safety Objective: Lead complication-free rate at 6 months

The Attain Stability Quad MRI SureScan LV Lead (Model 4798) will be considered safe if the probability of subjects free of Model 4798 lead-related complications at 6 months post-implant is greater than 87% (i.e., the lower bound of a one-sided 97.5% confidence interval must be greater than 87%).

Primary Efficacy Objectives: Lead pacing capture thresholds at 6 months

To demonstrate the effectiveness of the Attain Stability Quad MRI SureScan LV Lead (Model 4798), the study will evaluate the likelihood that there are at least two programmable vectors for each patient post implant. The effectiveness of this lead will be evaluated based on two primary efficacy objectives. More specifically, both primary efficacy objectives must be met simultaneously.

Primary Efficacy Objective #1

The Attain Stability Quad MRI SureScan LV Lead (Model 4798) will meet this objective if the proportion of subjects with at least one LV lead pacing vector having a pacing capture threshold less than or equal to 2.5 V at 0.5 ms pulse width at 6 months post-implant is greater than 80% (i.e., the lower bound of a one-sided 97.5% confidence interval must be greater than 80%).

Primary Efficacy Objective #2

The Attain Stability Quad MRI SureScan LV Lead (Model 4798) will meet this objective if the proportion of subjects with at least one additional (or second) LV lead pacing vector having a pacing capture threshold less than or equal to 4.0 V at 0.5 ms pulse width at 6 months post-implant is greater than 80% (i.e., the lower bound of a one-sided 97.5% confidence interval must be greater than 80%).

11.1.2. Secondary Objective(s)

The secondary objectives are descriptive in nature and are intended to provide additional information about the Attain Stability Quad MRI SureScan LV Lead (Model 4798). There will be no established performance requirements for these secondary objectives.

- To summarize implant procedure related information: success rate, implant related times
- To estimate 6-month reliability: post implant lead failure modes (i.e. complication rate)
- To estimate electrical measurement values (Pacing Capture Thresholds (PCTs) and Lead Impedance) at 6 months post-implant

11.2. Endpoints

11.2.1 Primary Endpoints

Primary Safety Endpoint

The study primary safety endpoint is Attain Stability Quad MRI SureScan LV Lead (Model 4798) related complications through 6 months post implant. All reported system and procedure-related AEs will be reviewed by an event review committee for LV lead relatedness and severity (complication vs observation, refer to 17.1.2 for definitions).

Primary Efficacy Endpoint #1

The Model 4798 LV lead has sixteen (16) programmable pacing configurations. The endpoint for the primary efficacy objective is whether or not there is at least one Model 4798 LV lead pacing vector with pacing capture voltage thresholds less than or equal to 2.5V. This endpoint will be measured at the 6-month post implant follow-up visit.

Primary Efficacy Endpoint #2

The co-primary efficacy endpoint is whether or not a second Model 4798 lead configuration has a pacing capture threshold less than or equal to 4V, excluding the pacing vector that is already counted to the primary efficacy endpoint #1. This endpoint will be measured at 6-month post implant follow-up visit.

11.2.2 Secondary Endpoints**To summarize implant procedure related information**

Implant procedure related endpoints will include implant success rate and procedure durations.

To estimate 6-month reliability

The Model 4798 LV lead 6-month reliability endpoint is Model 4798 lead related complications.

To estimate electrical measurement values (Pacing Capture Thresholds (PCTs) and Lead Impedance) at 6 months post-implant

The electrical measurements are pacing capture thresholds and impedance values for the four extended bipolar configurations, i.e. LV1 to RVCoil, LV2 to RV Coil, LV3 to RV Coil and LV4 to RV Coil (refer to 15.8.2.3 for the testing procedure requirements).

[figure not shown]
12. Study Design

The Attain Stability Quad Clinical Study is a prospective, non-randomized, multi-site, Investigational Device Exemption (IDE), interventional clinical study. The purpose of this clinical study is to evaluate the safety and efficacy of the Attain Stability Quad MRI SureScan LV Lead (Model 4798) in patients indicated for a de novo LV lead implant. This will be assessed through a primary safety and primary efficacy endpoints.

All subjects included in the study will be implanted with a Medtronic market released CRT-P or CRT-D device and an Attain Stability Quad MRI SureScan LV Lead (Model 4798). For de novo CRT systems, compatible market released Medtronic RA and Medtronic RV leads will be required. For subjects enrolled who are receiving an upgrade to a CRT system, existing non-Medtronic RV and/or existing non-Medtronic RA leads that are not recalled, market withdrawn, and/or have a medical alert may be used.

Up to 471 subjects will be enrolled into the study and up to 471 Attain Stability Quad MRI SureScan LV Lead (Model 4798) implanted, to ensure a minimum effective sample size of 400 Model 4798 leads implanted with 6 months post implant follow up visits (assuming 15% attrition). For the secondary endpoint of individual lead failure modes, Bayesian methods utilizing data from up to 37 historical patients will be used. All other objectives will be analyzed using only patients enrolled in this study. After a successful implant, threshold testing will occur to show one LV vector with pacing capture threshold (PCT) ≤ 2.5 [contact] and with sufficient safety margin was programmed. Subjects will then be followed at implant, three months, six months and every six months thereafter until FDA approval is obtained or until study closure, whichever comes first.

The study will look to collect the following information: demographics, medical history, standard physical, NYHA class, implanted device information, pacing capture thresholds, device interrogations or save-to-media, medications, adverse events, system modifications, device deficiencies, and exit information. See Figure 1 and Section 15 for further detail on study procedures and data collection as well as time-points for data collection.

Figure 1: Study Visits

The study is expected to be conducted at up to 50 sites worldwide. Participating geographies are expected to include, but are not limited to: the United States, Canada, EMEA, Malaysia, and Hong Kong. To ensure a widespread distribution of data and to minimize site bias in the study results, the maximum number of subjects allowed at a single site is 50 subjects.

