15.8.2.1. Venogram

An occlusive venogram is required for venous visualization of the subject's coronary vasculature and will be used to pre-determine a desired target pacing location prior to placing the Attain Stability Quad MRI SureScan LV Lead (Model 4798). Once the pre-determined target pacing location is determined, a venous image will be collected. A copy of the venous image will be submitted to Medtronic and kept on file at the center.

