In an event that one Attain Stability Quad MRI SureScan LV Lead (Model 4798) is determined to be not suitable for a patient after the initial lead insertion; the implanting physician must assess the onset of any potential AEs. A second Attain Stability Quad MRI SureScan LV Lead (Model 4798) may only be introduced upon confirmation that no system-related AEs resulted from the first Attain Stability Quad MRI SureScan LV Lead (Model 4798) implant attempt. Any LV lead related AE observed during the initial LV lead attempt prohibits an attempt of a second Attain Stability Quad MRI SureScan LV Lead (Model 4798).

If the subject does not have a successful Attain Stability Quad MRI SureScan LV Lead (Model 4798) implant at the conclusion of the initial implant procedure, the subject should be followed until procedure or system related AEs are resolved or are unresolved with no further actions planned, whichever occurs later.

If an attempt to implant the Attain Stability Quad MRI SureScan LV Lead (Model 4798) does not occur, or if the Model 4798 LV lead cannot be implanted, the reasons why the lead was not attempted or attempted but not implanted must be documented on the Implant and Study Exit CRF. See additional definitions below.

No Attain Stability Quad MRI SureScan LV Lead (Model 4798) Attempted (lead not inserted into the body)

An Attain Stability Quad MRI SureScan LV Lead (Model 4798) attempt is defined as any time a Model 4798 lead is introduced into the body. Subjects that do not have an Attain Stability Quad MRI SureScan LV Lead (Model 4798) implant attempted will be exited from the study following their implant procedure

unless another Attain Stability Quad MRI SureScan LV Lead (Model 4798) attempt is scheduled. Adverse events, device deficiencies and deviations must be documented before the subject is exited.

Attain Stability Quad MRI SureScan LV Lead (Model 4798) Attempted but Not Implanted

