16.3. Potential Benefits

The potential benefits of having the Attain Stability Quad MRI SureScan LV Lead (Model 4798) implanted are similar to other LV leads currently available to the public. The Attain Stability Quad MRI SureScan LV Lead (Model 4798) is expected to increase lead stability and reduce the need for patients to undergo an additional procedure to replace a dislodged/displaced lead. Due to the active fixation helix, it may be possible to place the lead in veins of various sizes. There is a possibility that the Attain Stability Quad MRI SureScan LV Lead (Model 4798) may offer no additional benefit over similar LV leads. The information gained from this study could result in the improved management of other CRT patients.

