19.2. Secondary Objectives

19.2.1. Secondary Objective # 1

Objective - Implant procedure related information: success rate, implant related times

The Attain Stability Quad LV lead implant success rate will be estimated as the number of subjects with Attain Stability Quad MRI SureScan LV Lead (Model 4798) successfully implanted divided by the total number of subjects who had a Attain Stability Quad MRI SureScan LV Lead (Model 4798) implant attempt. A 2-sided 95% Confidence Interval will be calculated using the Exact Binomial method.

The distribution of implant related times will be summarized through statistical summaries such as mean, standard deviation, minimum, median and maximum. Only subjects with the Attain Stability Quad MRI SureScan LV Lead (Model 4798) successfully implanted will be included in this calculation. The total implant time is defined as time from initial incision to final skin closure. Fluoroscopy time is defined as the total time the fluoroscope is imaging. Cannulation time is defined as the time from insertion of the first CS cannulation catheter to the first successful CS cannulation. Successful lead placement time is defined as the time from lead insertion of the successfully placed lead to the time when the lead is placed in its first acceptable pacing location.

19.2.2. Secondary Objective # 2

Objective - 6-month reliability: post implant lead failure modes

The Attain Stability Quad MRI SureScan LV Lead (Model 4798) is a composite of two existing market released Medtronic products. The helix fixation is identical to the Attain Stability LV Lead Model 20066/4796 (market released outside of the US). The remainder of the lead is similar to the Attain Performa LV Lead Model 4298, released worldwide.

Historical datasets will be used as informative priors for lead related complications. More specifically, analysis of all complications related to fixation (helix performance) will use data from the Attain Stability (Model 20066/4796) research study, conducted outside of the US. Analysis of all other lead related complications will use data from the Attain Performa clinical study, conducted globally. Credible intervals will be constructed for each individual failure mode within the two groups.

Historical Data (for secondary endpoints only)

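### The implant success rate in Section 19.2.1 is a per-attempt figure; a rate over all subjects taken to a CRT implant procedure should stand beside it

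*Protocol*

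**What the plan says.** Section 11.2.2 only names the endpoint: "Implant procedure related endpoints will include implant success rate and procedure durations". The definition is in Section 19.2.1, where the number of subjects successfully implanted is "divided by the total number of subjects who had a Attain Stability Quad MRI SureScan LV Lead (Model 4798) implant attempt", with a two-sided exact 95% interval. Section 15.8.2.2 says when a subject enters that denominator: an "attempt is defined as any time a Model 4798 lead is introduced into the body". The same section says that subjects without a 4798 "implant attempted will be exited from the study following their implant procedure", unless another attempt is scheduled.

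The venogram comes before that point. Section 15.8.2.1 states: "An occlusive venogram is required for venous visualization". The image "will be used to pre-determine a desired target pacing location prior to placing" the lead.

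Both protocol versions in the file carry the same denominator and the same definition of an attempt.

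**The concern.** The denominator opens only after the operator has seen the coronary veins and chosen to introduce the lead. That choice is made after enrolment and may well be related to the chance of success. A subject whose veins look unpromising, and in whom the lead is never introduced, counts neither as a success nor as a failure. The rate therefore depends partly on how ready each operator is to try, across up to 56 sites.

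The rationale for active fixation is partly anatomical. Section 10.1 calls it advantageous in wide vessels or those with short take-offs, and Section 16.3 says: "Due to the active fixation helix, it may be possible to place the lead in veins of various sizes". A reader of the report is likely to take the success rate as the chance of leaving a planned procedure with this lead in place, and the defined rate does not estimate that.

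**Working it through.** **The sequence in the text**

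1. Enrolment is at signature of the consent form (Section 15.6).
2. Section 14.4 excludes only venous anatomy already known to be inadequate. Anatomy first seen on the study venogram therefore arises in subjects already enrolled.
3. The venogram is mandatory and precedes lead placement (Section 15.8.2.1).
4. An attempt, and so the denominator, begins when the lead enters the body (Section 15.8.2.2).
5. Section 15.16.2 expressly recognises subjects who have a CRT procedure without a 4798 attempt, and exits them unless an attempt is scheduled.
6. Section 19 plans no rate that includes them.

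**Formula**

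Let N be the subjects in whom the CRT procedure is started, A those with a 4798 attempt, and x those implanted. Write s = x/A for per-attempt success and f = (N − A)/N for the share not attempted.

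- Planned rate: x/A = s
- Rate over started procedures: x/N = s × (1 − f)
- Gap: s × f

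Because A cannot exceed N, x/A is never below x/N. It is higher as soon as one subject is not attempted (given at least one success).

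**Inputs**

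The protocol states no expected success rate, and Table 18 gives NA for Secondary Objective #1, so there is no planned figure to reproduce. N = 471 is the maximum enrolment from Table 18 (400/0.85 = 470.6, rounded up) and is used only for illustration, since the gap depends on s and f and not on N. Both s (about 95%) and f (0% to 10%) are assumptions.

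| Not attempted | A | x | x/A (exact 95% CI) | x/N (exact 95% CI) | Gap, points |
|---|---|---|---|---|---|
| 0 | 471 | 447 | 94.9% (92.5 to 96.7) | 94.9% (92.5 to 96.7) | 0 |
| 5 (1%) | 466 | 443 | 95.1% (92.7 to 96.8) | 94.1% (91.5 to 96.0) | 1.0 |
| 14 (3%) | 457 | 434 | 95.0% (92.5 to 96.8) | 92.1% (89.3 to 94.4) | 2.8 |
| 24 (5%) | 447 | 425 | 95.1% (92.6 to 96.9) | 90.2% (87.2 to 92.8) | 4.8 |
| 47 (10%) | 424 | 403 | 95.0% (92.5 to 96.9) | 85.6% (82.1 to 88.6) | 9.5 |

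The assumed s matters little. For s from 90% to 98%, the gap runs from 0.95 to 1.04 points at 1% not attempted, from 4.58 to 4.99 at 5%, and from 9.0 to 9.8 at 10%.

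The planned interval covers sampling error only and gives no sign of this gap. With 24 subjects not attempted, the rate over started procedures (90.2%) lies below the lower limit of the per-attempt interval (92.6%).

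**The case against.** The strongest reply is that nothing here is miscalculated. The denominator and the definition of an attempt are explicit and agree with each other, and a per-attempt rate has its own rationale: it keeps failed coronary sinus access, which happens before the lead is used, out of a figure about the lead. That stands, and it is why the per-attempt rate should be kept. A reader might infer that the planned rate is wrong or inflated. It is neither as defined; it is high only if read as success among subjects taken to implant.

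A reader might also infer that these subjects disappear. They do not. Section 15.8.2.2 requires the reason for no attempt on the Implant and Study Exit CRF, and adverse events, device deficiencies and deviations must be documented before exit. Subjects brought back for a scheduled attempt do enter the denominator.

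That operators will decline the lead because of the venogram is an inference from the order of events. The stated purpose of the image is to choose a target, and not every non-attempt will be anatomical.

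The 13 of 490 procedures with inability to implant an LV lead, in the single-centre series tabulated in Appendix 1, might look like a ready estimate of f. It is not. It counts failed placement and does not separate leads never introduced from leads tried without success, and the latter already count as failures in this protocol's rate.

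Nor should the point be stretched into a test of vein size. No objective evaluates it, Section 16.3 claims only a possibility, and neither denominator would settle it.

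Finally, a disposition table or a supplementary rate could appear in an SAP that is not shown. The denominator, however, is fixed in the protocol itself.

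**Conclusion.** The point holds in a limited form. The rate in Section 19.2.1 is conditional on an operator decision made after enrolment and after a mandatory venogram, so it is an upper bound on success among subjects taken to a CRT implant procedure. The direction follows from the definitions. The size does not, because the share not attempted is nowhere in the protocol; if no subject goes without an attempt, the two rates coincide. Section 11.1.2 makes the secondary objectives descriptive with no performance requirement, so neither the primary objectives nor any pass/fail conclusion is touched. This is a cheap improvement to reporting, not a correction of an error.

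**What to change.** In Section 19.2.1, keep the per-attempt rate and label it as such. Beside it add the number of subjects with a 4798 implanted divided by all consented subjects in whom the CRT implant procedure was started, with its exact two-sided 95% interval. Count a subject with a later scheduled attempt once, by final outcome. Define the start of the procedure; initial incision would do, as Section 19.2.1 already uses it to start total implant time.

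Tabulate the reasons for no attempt from the Implant and Study Exit CRF, separating failed coronary sinus access from a vein judged unsuitable for the lead.

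The cost is one more rate and one short table. The reasons are already required on the CRF, though its categories should be checked to confirm that they allow this split. The downside is a slightly less favourable descriptive figure.

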12.1. Duration

The study duration is expected to be approximately 19 months. This represents 13 months for subject enrollment and 6 months for subject follow-up for the last subject enrolled. Subjects are anticipated to be in the study for on average 12 months. The first enrollment is projected to occur in May 2017. Subjects will complete visits at enrollment/baseline, implant, 3 months, 6 months, and then every 6 months thereafter. Subjects will not be replaced with newly enrolled subjects upon early exit. As described in Section 19, the sample size accounts for attrition.

